1.3. Summary of Clinical Experience

In this ongoing Phase 1 study, as of 27 August 2021, a total of 27 subjects have been dosed and have completed the study. Seven subjects have received 1 mg KRP-A218 or placebo under fasted conditions (Group A1), 8 male subjects have received 3 mg KRP-A218 or placebo under fasted and fed conditions (Group A2a), 4 female subjects have received 3 mg KRP-A218 or placebo under fasted conditions (Group A2b), and 8 subjects have received 6 mg KRP-A218 or placebo under fasted conditions (Group A3). For dose escalation decision, a minimum of 6 subject's data per group has been evaluated, including 7 subjects in Group A1 (1 mg), 6 subjects in Group A2a (3 mg), and 8 subjects in Group A3 (6 mg). There were no serious adverse events (SAEs), deaths, or no other significant adverse events (AEs). The AEs experienced by these subjects have included headache, loose stools, cold symptoms, aching lower legs, abdominal pain, stomach ache, drowsiness, blood visible when passing stool sample, and sore throat. All were transient and either mild or moderate in severity.

Preliminary PK parameters determined from the ongoing Phase 1 study are presented in [Table 3](#).

Table 3: Geometric Mean (CV%) PK Parameters of CCI Following Single Oral Dose Administration of KRP-A218 to Healthy Subjects*

Parameter (units)	1 mg [Fasted]	3 mg [Fasted]	3 mg [Fed]	6 mg [Fasted]
AUC _{0-tlast} (ng·h/mL)	198 (18.5)	540 (27.0)	570 (25.6)	1160 (28.4)
AUC _{0-∞} (ng·h/mL)	210 (18.6)	564 (30.1)	596 (28.0)	1230 (28.4)
AUC _{0-24h} (ng·h/mL)	145 (19.5)	388 (21.4)	393 (19.1)	813 (27.9)
C _{max} (ng/mL)	11.9 (30.3)	29.8 (23.5)	29.5 (15.2)	60.3 (26.5)
t _{max} ** (h)	3.00 (2.00-4.00)	3.50 (2.00-4.00)	3.50 (3.00-8.00)	3.50 (1.50-4.00)
t _{1/2} (h)	18.2 (11.5)	15.2 (20.3)	14.8 (18.4)	16.9 (9.68)

Abbreviations: AUC_{0-∞} = area under the concentration-time curve from time 0 extrapolated to infinity; AUC_{0-24h} = area under the concentration-time curve from time 0 to 24 hours; AUC_{0-tlast} = area under the concentration-time curve from time 0 to the time of the last quantifiable concentration; C_{max} = maximum observed concentration; CV% = coefficient of variation; PK = pharmacokinetic; t_{1/2} = apparent terminal elimination half-life; t_{max} = time of the maximum observed concentration.

* As per protocol, a minimum of 6 subjects (4 active subjects) data per group was evaluated for dose escalation decision.

** Median (min-max)

Following oral administration of KRP-A218, maximum concentrations of CCI were attained 3.0 to 3.5 hours postdose (median time to maximum observed concentration [t_{max}]), thereafter declining with a geometric mean half-life (t_{1/2}) of approximately 15 to 18 hours. Systemic exposure to CCI (maximum observed concentration [C_{max}] and area under the concentration-time curve from time 0 to 24 hours [AUC_{0-24h}]) increased in an approximate dose proportional manner over 1 to 6 mg KRP-A218. Administration of KRP-A218 following a high fat meal had no effect on the rate and extent of absorption of CCI.

1.4. Study Rationale

This is the first time KRP-A218 will be administered to humans. The principal purposes of this study are to evaluate the safety and tolerability data when KRP-A218 is administered orally as single and multiple doses to healthy subjects. This information, together with the PK data, will help establish the doses and dosage regimen suitable for administration to patients. The study will also investigate the effects of food and sex on the PK of CCI prior to patient studies.

This first-in-human study also incorporates a DDI study. The initial target population of KRP-A218 includes immunocompromised patients, such as HCT recipients who require concomitant azole antifungal drugs to reduce the risk of fungal infection. Preclinical studies have shown that CYP3A4 is the major metabolic enzyme of CCI, and the presence and magnitude of DDI with CYP3A4 inhibitors, even if exploratory, should be confirmed early in development to understand the potential risk leading to dose adjustments or contraindications due to DDI. It is important to confirm the assessment of the impact of the combination of KRP-A218 and itraconazole, as an appropriate and potent CYP3A4 inhibitor, on PK as this will provide very important information for subsequent study design and dose selection for phase 2 and phase 3 studies.

1.5. Benefit-risk Assessment

Healthy subjects in the current study will not receive any health benefit (beyond that of an assessment of their medical status) from participating in the study. The risks of participation are primarily those associated with adverse reactions to the investigational medicinal product (IMP), although there may also be some discomfort from collection of blood samples and other study procedures. More information about the known and expected risks and reasonably anticipated AEs associated with KRP-A218 may be found in the Investigator's Brochure (IB).[\[18\]](#)

2. OBJECTIVES AND ENDPOINTS

2.1. Objectives

Parts A and B:

The primary objective is:

- to evaluate the safety and tolerability of single and multiple oral doses of KRP-A218 in healthy subjects.

The secondary objectives are:

- to assess the PK of CCI (the active ingredient of KRP-A218) following single and multiple oral doses of KRP-A218 in healthy subjects.
- to assess the effect of food on the PK of CCI following a single oral dose of KRP-A218 in healthy male subjects.
- to assess the effect of sex on the PK of CCI following a single oral dose of KRP-A218.

The exploratory objectives are:

- to explore blood and urine samples for the metabolite profiles of CCI following single and multiple oral doses of KRP-A218 in healthy male subjects.
- to explore faecal samples for the metabolite profiles following a single oral dose of KRP-A218 in healthy male subjects.
- to explore blood and urine samples for pharmacodynamic biomarkers.
- to explore a potential effect of KRP-A218 on phospholipid-C in serum and faecal calprotectin.
- to collect blood samples for potential pharmacogenetic analyses.
- to collect continuous ECG waveforms for concentration-QTc analysis, following single oral doses of KRP-A218 in healthy subjects (Part A only).

Part C:

The primary objective is:

- to assess the effect of multiple doses of itraconazole (cytochrome P450 3A4 inhibitor) on the single-dose PK of CCI in healthy male subjects.

The secondary objectives are:

- to assess the safety and tolerability of single oral doses of KRP-A218 when co-administered with multiple oral doses of itraconazole in healthy male subjects.
- to assess the PK of itraconazole and its metabolite hydroxy-itraconazole when co-administered with KRP-A218 in healthy male subjects.

The exploratory objectives are:

- to explore blood samples for the metabolite profiles of CCI administered KRP-A218 alone and when co-administered with itraconazole in healthy male subjects.
- to explore a potential effect of KRP-A218 on phospholipid-C in serum and faecal calprotectin.
- to collect blood samples for potential pharmacogenetic analyses.

2.2. Endpoints

2.2.1. Primary Endpoints

For Parts A and B, the safety and tolerability endpoints are as follows:

- AEs
- body weight

- clinical laboratory evaluations (haematology, clinical chemistry [with the exception of phospholipid-C], urinalysis, coagulation, and faecal occult blood)
- 12-lead ECG parameters
- vital signs (blood pressure, pulse rate, respiratory rate, and oral body temperature)
- Bristol Stool Chart
- physical examinations

For Part C, the DDI (KRP-A218 alone versus co-administered with itraconazole) assessment, the PK endpoints will be the parameters derived from plasma concentrations of CCI on Days 1 and 11, which are as follows:

- area under the concentration-time curve (AUC) from time 0 extrapolated to infinity ($AUC_{0-\infty}$)
- AUC from time 0 to the time of the last quantifiable concentration ($AUC_{0-t_{last}}$)
- C_{max}
- t_{max}
- apparent terminal elimination half-life ($t_{1/2}$)
- apparent total clearance (CL/F)
- apparent volume of distribution during the terminal phase (V_z/F).

Other PK parameters may also be added.

2.2.2. Secondary Endpoints

For Part A, the single ascending dose, food (fed versus fasted dietary status at dosing), and sex (male versus female) PK parameters derived from plasma concentrations of CCI on Day 1 (including Day 1 in Treatment Period 2) are as follows:

- $AUC_{0-\infty}$
- $AUC_{0-t_{last}}$
- C_{max}
- t_{max}
- $t_{1/2}$
- CL/F
- V_z/F .

For Part B, the multiple ascending dose PK parameters derived from plasma concentrations of CCI on Days 1 and 14 are as follows:

- $AUC_{0-\tau}$
- $AUC_{0-\infty}$ (Day 1 only)

- $AUC_{0-t_{last}}$
- C_{max}
- minimum observed concentration (C_{min})
- t_{max}
- $t_{1/2}$
- CL/F
- V_z/F
- observed accumulation ratio based on $AUC_{0-\tau}$ ($AR_{AUC0-\tau}$)
- observed accumulation ratio based on C_{max} during the dosing interval (AR_{Cmax}).

For Part C, the safety and tolerability endpoints are as follows:

- AEs
- body weight
- clinical laboratory evaluations (haematology, clinical chemistry [with the exception of phospholipid-C], urinalysis, coagulation, and faecal occult blood)
- 12-lead ECG parameters
- vital signs (blood pressure, pulse rate, respiratory rate, and oral body temperature)
- Bristol Stool Chart
- physical examinations.

For Part C, the PK parameters derived from plasma concentrations of itraconazole and hydroxy-itraconazole on Day 11 are as follows:

- $AUC_{0-\tau}$
- C_{max}
- t_{max} .

Other PK parameters may also be added.

2.2.3. Exploratory Endpoints

For Parts A, B, and C, the exploratory endpoints that will be reported in the CSR for this study are:

- Phospholipid-C
- Faecal calprotectin

The endpoints associated with the exploratory metabolite profiling, biomarker analysis, pharmacogenetic analysis, and concentration-QTc analysis will be reported elsewhere, as applicable.

3. INVESTIGATIONAL PLAN

This Phase 1 study will consist of 3 parts, Parts A, B, and C. Part A will comprise a double-blind, randomised, placebo-controlled, single-dose, sequential-group, escalating-dose design, enrolling healthy male and female subjects (female subjects in Group A2b only). Part A will include a sex-effect (Groups A2a and A2b) which will investigate the effect of sex on PK of CCI [REDACTED] by comparing PK parameters following dosing in females versus dosing in males. Part A will also include a food-effect Group A2a which will be a 2-period arm to investigate the effect of food on PK of CCI [REDACTED] by comparing PK parameters following dosing in fed conditions versus dosing in fasted conditions.

Part B will comprise a double-blind, randomised, placebo-controlled, multiple-dose, sequential-group, escalating-dose design, enrolling healthy male subjects.

Part C will comprise an open-label, fixed-sequence, enrolling healthy male subjects to investigate the effect of multiple oral doses of itraconazole on the single oral dose PK of CCI [REDACTED] in healthy male subjects.

3.1. Overall Study Design and Plan

3.1.1. Part A (Single Ascending Dose Study)

Part A will comprise a double-blind, randomised, placebo-controlled, single-dose, sequential-group, escalating-dose study incorporating a single-group, 2-period arm to investigate the effect of food on the PK of CCI [REDACTED]. Part A will also include a sex-effect arm (Groups A2a and A2b) which will investigate the effect of sex on PK of CCI [REDACTED] by comparing PK parameters following dosing in females versus dosing in males. Overall, 48 subjects will be studied in 5 groups (Groups A1 to A5); Groups A1, and A3 to A5 will consist of 8 male subjects, and Group A2 will consist of 16 subjects split into 2 subgroups (Group A2a [male subjects only] and Group A2b [female subjects only]) that will consist of 8 subjects each.

Potential subjects will be screened to assess their eligibility to enter the study within 28 days prior to the first dose administration. Each subject will participate in 1 treatment period only, except for Group A2a, where each subject will participate in 2 treatment periods where doses of KRP-A218 will be separated by an interval of 7 to 10 days (up to and including Day -1 of Treatment Period 2). The washout period may be extended depending on the observed $t_{1/2}$ of CCI [REDACTED]. Subjects will reside at the study site from Day -1 (the day before dosing) to Day 4 of each treatment period.

All subjects will return for a follow-up visit 7 to 10 days after their final dose. The follow-up period may be extended depending on the observed $t_{1/2}$ of CCI [REDACTED].

Based on the ongoing review of the safety, tolerability, and PK results, additional nonresidential visits may be required. The number of additional visits per subject will not exceed 3 per period (as applicable) and will not extend beyond 28 days after each final dosing.

occasion. All subjects may stay in the clinical research unit (CRU) outside treatment periods due to COVID-19 risks.

[figure not shown]
In each of Groups A1 to A5, 6 subjects will receive KRP-A218 and 2 subjects will receive placebo in accordance with a randomisation schedule. In Groups A1, A2b, and A3 to A5, all doses will be administered in the fasted state on the morning of Day 1. For Group A2a, Period 1, Day 1 doses will be administered in the fasted state and Period 2, Day 1 doses will be given 30 minutes after starting a standard high-fat breakfast. Each subject in Groups A1, A2b, and A3 to A5 will receive only a single dose of KRP-A218 or placebo during the study. In Group A2a, subjects will have the same treatment in both periods, such that each subject will receive 2 single doses of KRP-A218 or placebo during the study.

All groups in Part A (with the exception of Group A2a in Treatment Period 2) will receive the IMP using a sentinel approach, as described in [Section 5.3](#). Details regarding dose escalation are presented in [Section 3.5](#).

An overview of the study design is shown in [Figure 1](#) and [Figure 2](#), and the planned dose levels in [Figure 5](#).

[figure not shown]
Schedules of Assessments is presented in [Appendix 6](#).

Figure 1: Study Schematic (Part A; Groups A1, A2b [Female subjects Only], and A3 to A5)

The follow-up period may be extended depending on the observed $t_{1/2}$ of **CCI**

Figure 2: Study Schematic (Part A; Group A2a [Male subjects Only])

The washout and follow-up periods may be extended depending on the observed $t_{1/2}$ of CCI [REDACTED]

The total duration of study participation for each subject (from screening through follow-up visit) is anticipated to be up to 39 days (Groups A1, Group A2b [female subjects only], A3 to A5) or up to 50 days (Group A2a; male subjects only).

3.1.2. Part B (Multiple Ascending Dose Study)

Part B will comprise a double-blind, randomised, placebo-controlled, multiple-dose, sequential-group, escalating-dose design, enrolling healthy male subjects. Overall, 40 subjects will be studied in 4 groups (Groups B1 to B4), with each group consisting of 10 male subjects. Part B may start after completion of Group A3, at dose equal to or less than given in Groups A1 to A3.

Potential subjects will be screened to assess their eligibility to enter the study within 28 days prior to the first dose administration. Each subject will participate in 1 treatment period only and reside at the CRU from Day -1 (the day before dosing) until the morning of Day 17 (following assessments at 72 hours after final dosing).

All subjects will return for a follow-up visit 7 to 10 days after their final dose. The follow-up period may be extended depending on the observed $t_{1/2}$ of CCI [REDACTED]

In each of Groups B1 to B4, 8 subjects will receive KRP-A218 and 2 subjects will receive placebo in accordance with a randomisation schedule. The dietary state for dosing in Part B will be subject to review of the PK data from the fed/fasted comparison in Part A. For all subjects, dosing will occur on Days 1 to 14. The planned dosing frequency is once per day, however the dosing frequency in Part B may be changed following review of data from groups in Part A ([Section 3.4](#)). On Day 14, the last dose will be the morning dose regardless of the dosing frequency (QD, BID, TID).

[figure not shown]
The total daily dose administered will not exceed an exposure shown to be safe and well tolerated in Part A.

Based on the ongoing review of the safety, tolerability, and PK results, additional nonresidential visits may be required. The number of additional visits per subject will not exceed 3 and will not extend beyond 28 days after each final dosing occasion. All subjects may stay in the CRU even outside treatment period due to COVID-19 risks.

All groups in Part B will receive the IMP using a sentinel approach, as described in [Section 5.3](#). Details regarding dose escalation are presented in [Section 3.5](#).

An overview of the study design is shown in [Figure 3](#), and the planned dose levels in [Figure 5](#).

A Schedule of Assessments is presented in [Appendix 6](#).

Figure 3: Study Schematic (Part B)

The follow-up period may be extended depending on the observed $t_{1/2}$ of CCI.

The total duration of study participation for each subject (from screening through follow-up visit) is anticipated to be up to 52 days.

3.1.3. Part C (Drug-Drug Interaction Study)

Part C will comprise an open-label, fixed-sequence, enrolling healthy male subjects to investigate the effect of multiple oral doses of itraconazole on the single oral dose PK of CCI in healthy subjects. There will be 1 group; Group C1, consisting of 12 male subjects. Part C will start after completion of blinded safety, tolerability, and PK data review in Part A. All subjects will receive each of the following treatments:

- Days 1 and 11: single oral dose of KRP-A218
- Day 4: 2 \times single oral doses of 200 mg itraconazole, approximately 12 hours apart
- Days 5 to 13: single oral doses of 200 mg itraconazole

The study days of dosing of itraconazole and KRP-A218 may be amended to extend the interval between the first dose of KRP-A218 and the first dose of itraconazole depending on the observed $t_{1/2}$ of CCI.

Potential subjects will be screened to assess their eligibility to enter the study within 28 days prior to the first dose administration. Subjects will be admitted into the study site on Day -1 and be confined to the study site until discharge on Day 14.

Subjects will return to the study site for a follow-up visit 7 to 10 days after the last dose of KRP-A218. The follow-up period may be extended depending on the observed $t_{1/2}$ of CCI.

[figure not shown]
Based on the ongoing review of the safety, tolerability, and PK results, additional nonresidential visits may be required. The number of additional visits per subject will not exceed 3 and will not extend beyond 28 days after each final dosing occasion. All subjects may stay in the CRU even outside treatment period due to COVID-19 risks.

The dietary state for dosing of KRP-A218 alone on Day 1 and KRP-A218 co-administered with itraconazole on Day 11 will be determined by comparing the PK data between fed and fasted state in Group A2a. Itraconazole on Days 4 to 10, 12 and 13 will be administered in the fasted state. The dose level of KRP-A218 will be confirmed based on the available safety, tolerability, and PK data in preceding Parts A and/or B of the study.

An overview of the study design is shown in [Figure 4](#), and the planned dose levels in [Figure 5](#).

[figure not shown]
A Schedule of Assessments is presented in [Appendix 6](#).

Figure 4: Study Schematic (Part C)

The study days of dosing of itraconazole and KRP-A218 may be amended to extend the interval between the first dose of KRP-A218 and the first dose of itraconazole depending on the observed $t_{1/2}$ of CCI. In addition, the follow-up period may be extended depending on the observed $t_{1/2}$ of CCI.

The total duration of study participation for each subject (from screening through follow-up visit) is anticipated to be up to 49 days.

Figure 5: Planned Dose Levels of KRP-A218 (Parts A, B, and, C)

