Systemic exposure to CCI [REDACTED] following single or repeated oral dosing with CCI [REDACTED] was established in mouse, rat, dog, and monkey. There were no remarkable differences in exposure with repeated dosing and between the sexes, although values in females were slightly higher than in males for rats. Blood-plasma concentration ratio of CCI [REDACTED] was similar across mouse, rat, dog, monkey, and human, with values of 0.909, 1.03, 0.933, 1.80, and 1.10, respectively, while plasma protein binding was 85.8, 75.6, 82.7, 79.7, and 88.4% in mouse, rat, dog, monkey, and human, respectively. CCI [REDACTED] was metabolized by CYP3A, CYP2C9, CYP2C8, and CYP2D6. The contribution ratio for CCI [REDACTED] metabolism was determined as ranging from 68.4 to 94.4% for CYP3A and was determined as ranging from 5.7 to 22.0% for CYP2C9. CCI [REDACTED] generally had low potential for inhibition although slight time dependent inhibition was observed for CYP3A4 and it was shown to have a potential to induce CYP1A2, CYP2B6, CYP2C9, and CYP3A4.

A core battery of central nervous system, respiratory and cardiovascular (CVS) studies with CCI [REDACTED] showed no safety concerns. CCI [REDACTED] was shown to have no genotoxic potential from evaluation in a bacterial reverse mutation test, an in vitro chromosome aberrations assay in Chinese hamster lung cells and a bone marrow micronucleus study in rats. In a 2-week good laboratory practice (GLP) oral toxicology study in the rat, the no observed adverse effect level (NOAEL) of CCI [REDACTED] was considered to be below 5 mg/kg/day for males (based on inflammatory cell infiltration in the lumen of the coagulating gland) and 5 mg/kg/day for

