Moreover, considering the individual AUC_{0-24h} values observed in Groups A1 to A3, it has been assumed that the maximum AUC_{0-24h} may be in the range of approximately 2-fold the mean AUC_{0-24h}. Therefore, it is considered reasonable to set the dose escalation criteria at the NOAEL equivalent exposure (maximum AUC_{0-24h} of 3930 ng·h/mL), which is approximately 2-fold of the estimated steady-state exposure at 8 mg (mean AUC_{0-24h}*R of 1730 ng·h/mL). In addition, based on safety data from this ongoing study at doses of 1 to 6 mg (Groups A1 to A3), no gastrointestinal findings of any concern have been observed.

Therefore, in this Phase 1 study, it is planned to investigate higher doses within the range up to the NOAEL (5 mg/kg in male rats: C_{max} 1220 ng/mL, AUC_{0-24h} 3930 ng·h/mL) as the maximum exposure for individuals.

Exploring these higher doses in a Phase 1 study will allow AEs to be more closely monitored than in Phase 2 or 3 studies.^[20] It will also allow the exploratory objective to collect data for concentration-QTc analysis to be more relevant as according to regulatory guidance, the QTc response should be characterised at a sufficiently high multiple of the clinically relevant exposure.^[21, 22, 23]

CCI was metabolized by CYP3A, CYP2C9, CYP2C8, and CYP2D6, and the contribution ratio of CYP3A was determined as ranging from 68.4 to 94.4%. Because of the high contribution ratio for CYP3A, co-administration of KRP-A218 with drugs that induce or inhibit CYP3A may affect the exposure of **CCI**. The dose level in Part C will be selected based on PK profile in preceding Parts A and/or B.

The proposed IMP dose levels for Parts A, B, and C are shown in [Table 5](#).

Table 5: Proposed Investigational Medicinal Product Dose Levels for Parts A, B, and C

Study Part	Group	Subject Numbers	Treatments	KRP-A218 Dose	Dietary State	Sex
Part A	A1	0101 – 0108	6 KRP-A218 2 placebo	1 mg	Fasted	Male
	A2a ^a	0109 – 0116	6 KRP-A218			
			2 placebo (2 doses)	3 mg	Fasted and Fed	Male
	A2b ^a	0117 – 0124	6 KRP-A218 2 placebo	3 mg	Fasted	Female
	A3	0125 – 0132	6 KRP-A218 2 placebo	6 mg	Fasted	Male
	A4	0133 – 0140	6 KRP-A218 2 placebo	12 mg	Fasted	Male
Part B	A5	0141 – 0148	6 KRP-A218 2 placebo	maximum dose of 24 mg	Fasted	Male
	B1	0201 – 0210	8 KRP-A218 2 placebo	X mg	Fasted/Fed ^b	Male
	B2	0211 – 0220	8 KRP-A218 2 placebo	X mg	Fasted/Fed ^b	Male

B3	0221 – 0230	8 KRP-A218 2 placebo	X mg	Fasted/Fed ^b	Male	

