7.1. Pharmacokinetic Assessments

7.1.1. Pharmacokinetic Sample Collection and Processing

Blood samples (approximately 1 × 2-mL sample per scheduled time) for PK analysis of CCI [REDACTED] and blood samples (approximately 1 × 2-mL sample per scheduled time) for PK analysis of itraconazole and its metabolite hydroxy-itraconazole will be collected by venepuncture or cannulation at the times indicated in the Schedule of Assessments in Appendix 6. Furthermore, up to 3 additional blood samples may be taken from each subject per treatment period in Part A, and up to 6 additional blood samples may be taken from each subject in Parts B and C, with the maximum volume of blood withdrawn per subject will not exceed the limit detailed in Appendix 3. Any changes to the scheduled times of PK assessments will be agreed with the Sponsor and documented in the TMF. Blood samples taken from subjects who received placebo will not be analysed.

Procedures for collection, processing, and shipping of PK blood samples will be detailed in a separate document.

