8.5.1.1. Criteria for the Calculation of Apparent Terminal Elimination Rate Constant and Half-life

The start of the terminal elimination phase for each subject will be defined by visual inspection and generally will be the first point at which there is no systematic deviation from the log-linear decline in concentrations.

The apparent terminal elimination rate constant (λ_z) will only be calculated when a reliable estimate can be obtained using at least 3 data points, preferably not including C_{max} , and the adjusted coefficient for determination of exponential fit (R^2 -adj) of the regression line is ≥ 0.7 . Parameters requiring λ_z for their calculation (eg, $AUC_{0-\infty}$, $t_{1/2}$, CL/F (single dose only), V_z/F) will only be calculated if the R^2 -adj value of the regression line is ≥ 0.7 .

The following regression-related diagnostic PK parameters will be determined where possible:

Parameter	Units	Definition
λ_z	1/h	apparent terminal elimination rate constant
λ_z Upper	h	end of exponential fit
λ_z Lower	h	start of exponential fit
λ_z N		number of data points included in the log-linear regression
λ_z Span Ratio		time period over which λ_z was determined as a ratio of $t_{1/2}$
R^2 -adj		adjusted coefficient for determination of exponential fit

Where possible, the span of time used in the determination of λ_z (ie, the difference between λ_z Upper and λ_z Lower) should be ≥ 2 half-lives. If the λ_z Span Ratio is < 2 , the robustness of the $t_{1/2}$ values will be discussed in the CSR.

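### Part C stops KRP-A218 sampling 72 h after the Day 11 dose; if itraconazole slows clearance strongly, the AUC0-tlast interaction ratio reads low and AUC0-inf can be dropped

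*Protocol*

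**What the plan says.** Part C is a fixed-sequence comparison in 12 men: "Days 1 and 11: single oral dose of KRP-A218", with itraconazole from Day 4 to Day 13. Protocol Table 12 schedules KRP-A218 samples from predose to 72 h after each dose. Protocol Appendix 3 confirms this with 32 samples, that is 2 profiles of 16. Table 12 and Appendix 3 are the evidence on sampling. The sentence in section 3.1.3, "Subjects will be admitted into the study site on Day -1 and be confined to the study site until discharge on Day 14", concerns confinement and shows only that residence ends at that same 72 h point. No PK sample is scheduled at the follow-up visit, 7 to 10 days after the last KRP-A218 dose.

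The half-life clause in section 3.1.3 says that dosing days "may be amended to extend the interval between the first dose of KRP-A218 and the first dose of itraconazole". A companion sentence allows a longer follow-up period. Neither extends the Day 11 profile. Section 7.1.1 does permit more sampling: "up to 6 additional blood samples may be taken from each subject in Parts B and C". Section 3.1.3 permits up to 3 extra visits within 28 days of dosing.

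On clearance, section 3.5 reports that "the contribution ratio of CYP3A was determined as ranging from 68.4 to 94.4" percent, and section 1.3 gives an uninhibited half-life "of approximately 15 to 18 hours".

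SAP 8.5.3.4 analyses AUC0-tlast, AUC0-inf and Cmax. SAP 8.5.1.2 lets AUC0-inf be left out, at discretion, when more than 20% is extrapolated. SAP 8.5.1.1 asks, where possible, that the span used for the terminal slope "should be ≥ 2 half-lives".

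**The concern.** The window suits Day 1, where 72 h is about four half-lives and some 6% of the AUC lies beyond the last sample. Day 11 differs by design, because the inhibitor is there to slow elimination. A slower Day 11 profile loses more of its area to the 72 h cut-off than the Day 1 profile does, so the AUC0-tlast ratio falls short of the true one.

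The SAP rules add to this. The larger the interaction, the more of the Day 11 AUC0-inf is extrapolated and the more readily it can be set aside, which leaves the truncated measure. SAP 8.5.1.2 names a fallback AUC for dose proportionality, food effect and sex effect, but not for the interaction.

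This ratio serves the primary objective of Part C. Section 1.4 links it to possible dose adjustment or contraindication in patients who need azoles, and to phase 2 and 3 design. An error here understates the interaction.

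**Working it through.** **Inputs.** Protocol Table 3, 6 mg fasted: half-life 16.9 h, median tmax 3.5 h, AUC0-tlast 1160 and AUC0-inf 1230 ng·h/mL. CYP3A share fm of 0.684 to 0.944 (sections 1.2 and 3.5). Window of 72 h (Table 12). Last itraconazole dose on Day 13, 48 h after the Day 11 dose. The degree of inhibition I is not given, so 50, 80 and 100% are assumed. The model also assumes that the CYP3A share of metabolism is the share of total clearance, and that bioavailability is unchanged.

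**Reproducing the protocol's own figures.** k = ln2/16.9 = 0.0410 per h. Accumulation ratio = 1/(1 − e^(−24k)) = 1.597 (Table 4: 1.6). Steady state at 8 mg = 813 × 8/6 × 1.597 = 1731 (Table 4: 1730). With first-order absorption set to give tmax 3.5 h (ka = 0.934 per h), the model puts 5.5% of the Day 1 AUC beyond 72 h. The observed figure is 1 − 1160/1230 = 5.7%.

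**Day 11.** True ratio ρ = 1/(1 − fm × I). Inhibited half-life = 16.9 × ρ.

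AUC(0–72) is proportional to ka/(ka − k) × [(1 − e^(−72k))/k − (1 − e^(−72ka))/ka], with k replaced by k/ρ on Day 11. The AUC0-tlast ratio is the Day 11 value over the Day 1 value.

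| I | fm | True ratio | Half-life (h) | Half-lives in 72 h | AUC0-tlast ratio | Day 11 extrapolated |
|---|---|---|---|---|---|---|
| 50% | 0.684 | 1.52 | 25.7 | 2.80 | 1.37 | 14.8% |
| 50% | 0.944 | 1.89 | 32.0 | 2.25 | 1.57 | 21.5% |
| 80% | 0.684 | 2.21 | 37.3 | 1.93 | 1.71 | 26.8% |
| 80% | 0.944 | 4.08 | 69.0 | 1.04 | 2.20 | 49.1% |
| 100% | 0.684 | 3.16 | 53.5 | 1.35 | 2.01 | 39.9% |
| 100% | 0.944 | 17.9 | 302 | 0.24 | 2.84 | 85.0% |

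Hand check without absorption, ρ = 3.16: 3.16 × (1 − 0.393)/0.948 = 2.02.

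**Why the ratio reads low.** AUC0-tlast ratio = AUC0-inf ratio × (1 − Day 11 extrapolated fraction)/(1 − Day 1 extrapolated fraction). For the fifth row: 3.16 × (1 − 0.399)/(1 − 0.055) = 2.01.

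**Where the SAP rules start to matter.** The 20% limit is reached at a true ratio of 1.81 (1.83 without absorption). Two half-lives no longer fit in 72 h above 36/16.9 = 2.13.

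**If bioavailability also rises.** With the effect split equally on the log scale between bioavailability and clearance, a true 3.16 reads 2.69 and a true 5 reads 3.85. With clearance alone they read 2.01 and 2.33.

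**What later samples recover.** If inhibition persisted, sampling Day 11 to 168 h or 240 h would give 2.80 or 3.02 for a true 3.16, 3.73 or 4.30 for a true 5, and 5.70 or 7.55 for a true 17.9. If inhibition is full to 72 h and then lost, anywhere from immediately to with a 96 h half-life (assumed), the fully sampled AUC0-inf ratio is 2.3 to 2.7, 2.8 to 3.6 and 3.5 to 5.3 respectively. All exceed the 72 h readings of 2.01, 2.33 and 2.84, and all remain below the truth.

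**The case against.** The case for leaving the schedule alone has several parts.

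- **The size is not fixed by the documents.** Section 3.4 says only that inhibition will be significant, and only if CYP3A4 carries much of human metabolism. The 68.4 to 94.4% comes from the nonclinical data. This stands, and is why the result is a range. A reader might infer from the CYP3A figures that 72 h covers only 0.2 to 1.4 inhibited half-lives. That needs complete inhibition, which is stated nowhere.
- **Other measures exist.** AUC0-tlast is one of seven Part C primary parameters, and AUC0-inf and Cmax are analysed with it. Where the slope span is short, the SAP asks for the half-life to be discussed in the report. This helps, but AUC0-inf can be dropped just when it is needed, and Cmax says little about a clearance effect.
- **The protocol is flexible.** Extra samples, extra visits and sponsor-agreed timing changes are allowed, and section 3.5 requires co-administered exposure to be predicted when the Part C dose is chosen. All true, but later sampling is optional and nothing triggers it from the Day 11 half-life.
- **The 72 h window roughly matches itraconazole cover.** Later samples see waning inhibition. This stands: it limits what later sampling can recover, and means AUC0-inf may be low as well.

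**Conclusion.** The point holds conditionally. If CYP3A inhibition is strong and acts mainly on clearance, the scheduled 72 h window makes the AUC0-tlast ratio read low. At 80% inhibition the shortfall runs from 2.2 read as 1.7 to 4.1 read as 2.2. At 50% it is modest, with 1.5 to 1.9 read as about 1.4 to 1.6. At 100%, true ratios from 3.2 to 18 are squeezed into 2.0 to 2.8. Above a true ratio of about 1.8 the AUC0-inf comparison is open to discretionary removal, and above about 2.1 the two half-life span cannot be reached in 72 h.

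A reader might go further and infer that the ratio settles near 2 to 3 whatever the true interaction. The documents do not support that. Below about 2.5-fold the ratio still follows the truth, at worst about 27% low (2.5 reads 1.82), and any rise in bioavailability lifts it. Nor does section 1.4 make Part C decisive for labelling: it allows that the assessment may be exploratory.

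The conclusion rests on a one-compartment model, the 6 mg half-life and the assumed degrees of inhibition. The gap itself, an unextended Day 11 profile, does not depend on the model. A change is worth making because it is cheap and reduces the bias in each scenario computed.

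**What to change.** 1. **Protocol Table 12 and section 3.1.3.** Schedule KRP-A218 samples later than 72 h after the Day 11 dose: at least one at the existing follow-up visit, with others drawn from the 6 extra samples and 3 extra visits already allowed. Extend the half-life clause to the Day 11 sampling window.
2. **SAP 8.5.3.4.** Report the AUC0-inf and AUC0-tlast ratios together. Do not remove a Day 11 AUC0-inf from the interaction analysis solely because extrapolation exceeds 20%; flag it and show the extrapolated fraction by day. State that the AUC0-tlast ratio is a lower bound when the Day 11 extrapolated fraction exceeds that of Day 1. State also that AUC0-inf may be low, because samples after the last itraconazole dose on Day 13 reflect waning inhibition.

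Cost: using all 6 extra samples adds 6 × 2 = 12 mL per subject, taking the Part C total from 211.9 to 223.9 mL against a 500 mL limit, plus a few sentences in the SAP. The late tail would only partly recover a very large interaction, so the reported ratio still needs the caveat.
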